### **8.4.2 Unanticipated Problem Reporting**

The investigator will report unanticipated problems (UPs) to the reviewing Institutional Review Board (IRB) and to the Data Coordinating Center (DCC)/lead principal investigator (PI). The UP report will include the following information:

- Protocol identifying information: protocol title and number, PI's name, and the IRB project number;
- A detailed description of the event, incident, experience, or outcome;
- An explanation of the basis for determining that the event, incident, experience, or outcome represents an UP;
- A description of any changes to the protocol or other corrective actions that have been taken or are proposed in response to the UP.

To satisfy the requirement for prompt reporting, UPs will be reported using the following timeline:

- UPs that are serious adverse events (SAEs) will be reported to the IRB and to the DCC/study sponsor within <insert timeline in accordance with policy> of the investigator becoming aware of the event.
- Any other UP will be reported to the IRB and to the DCC/study sponsor within <insert timeline in accordance with policy> of the investigator becoming aware of the problem.

All UPs should be promptly reported to appropriate institutional officials (as required by an institution's written reporting procedures), the supporting agency head (or designee), and the Office for Human Research Protections (OHRP).

## **9. Statistical Considerations**

### **9.1 Statistical Hypotheses**

- **Primary Efficacy Endpoints:**
  - Change of Protective Qi after a total of 12 weeks follow-up
- **Secondary Efficacy Endpoints:**
  - Change of Generic Qi after a total of 12 weeks follow-up
  - Change of Global Health (Appendix 5) including physical health and mental health after a total of 12 weeks follow-up
  - Change of saliva secretory IgA after a total of 12 weeks follow-up
  - Change of Emotional and Behavioral Dyscontrol (Appendix 6) after a total of 12 weeks follow-up
  - Change of Emotional Impact (Appendix 7) after a total of 12 weeks follow-up

### **9.2 Sample Size Determination**

A preliminary study was conducted prior to the current study for sample approximation [10]. We screened 47 volunteers and excluded those who were pregnant or planning to become pregnant, extremely ill, immune

deficient, taking medications/supplements known to affect Protective Qi status, or who consumed more than 28 g alcohol per day (i.e., the equivalent of more than 24 ounces of beer, 10 ounces of wine, or 3 ounces of distilled alcohol daily). 30 participants diagnosed with PQD were enrolled and treated with  $\beta$ -glucan in a dose of ~200 mg/day for 8 weeks. The PQD status (severity score) was monitored biweekly and used to estimate the effect size of  $\beta$ -glucan. Last Observation Carried Forward (LOCF) [15] imputation was used for handling missing data. When analyzing the data, we used matching techniques [11] to create a virtual control group that is essentially equivalent to the treatment group on observed pre-intervention characteristics. Nonetheless, any potential confounders were regarded as the effectors of Regression To Mean (RTM) [12] and were accounted for by Trochim's method ([13], P322) that adjusts an individual's pre-test score as follows:

$$x_{adj} = \bar{x} + r(x_{pre} - \bar{x}_{pre})$$

Where  $x_{adj}$  is the adjusted pretest value,  $\bar{x}_{pre}$  is the treatment group pre-test mean,  $r$  is the pre-post correlation of the severity score for the treatment group, and  $x_{pre}$  is the original pretest value. We then used Cohen's  $d$  ([14], P276) to calculate the treatment effect size.

$$d = 2 * f = 2 * \sqrt{\frac{\frac{SS(x_{post} - x_{pre}),}{SS(x_{post})}}{1 - \frac{SS(x_{post} - x_{pre}),}{SS(x_{post})}}} = 2 * \sqrt{\frac{\frac{7.479}{7.479 + 4.928}}{1 - \frac{7.479}{7.479 + 4.928}}} = 2 * 1.23 = 2.46$$

Where  $x_{post}$  is the post-treatment severity score, SS is the sum of square, and  $f$  is the F test on means in the analysis of variance and covariance.

Given the Cohen's  $d$  is a positively biased estimator of effect size when sample size are small [14], we adjusted Cohen's  $d$  to conventional "large effect size (0.8)".

Assuming an allowable Type I error (alpha) of 0.01 and power value of 0.9, we performed R package "pwr" and obtained a minimal sample size of 49 for each group.

### 9.3 Populations for Analyses

The intention-to-treat analysis method will be followed for trial outcomes. In the case of missing data due to participants that withdrew from the trial or missed visits, data from the previous visit will be used for the missing value (Last Observation Carried Forward, or LOCF).

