Enrollment will be initiated by a TCM practitioner. Note that the enrollment process may occur on the same day as the Screening Visit, or at a date not more than 14 days from the Screening Visit. If enrollment is performed on the same day as the screening visit, the enrollment process will begin with a basic physical examination (to be conducted by the Qualified Investigator, Q.I.; see Appendix 2) immediately following the screening process and continue as outlined below. Note that subjects that complete screening and enrollment on the same day will be considered to have completed both the Screening Visit and Study Visit 1. However, if subject enrollment cannot be completed during the Screening Visit (i.e., due to time restrictions or other circumstances), subjects will return to the clinic within 14 days to initiate the enrollment procedure. During this visit (Study Visit 1), the TCM practitioner will re-assess the subjects' PQD status (Appendix 4). If the potential subject does not exhibit PQD, they will not be enrolled in the study. If the potential subject continues to exhibit PQD, they will continue the

enrollment process. (Note that for purposes of data analysis, subjects' PQD status characterized during Study Visit 1 will supersede their PQD status characterized during the Screening Visit). As outlined above, the enrollment process begins with a basic physical exam of the head, ears, eyes, nose, throat, etc. performed by the Q.I. If, in the estimation of the Q.I., the potential subject is deemed not to be in good general health, they will not be enrolled in the study. If potential participants are deemed to be otherwise healthy by the Q.I., the enrollment procedure will continue. The enrollment will start in Dec. 2018 and concluded in March 2019.

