## **8. Study Assessments and Procedures**

### **8.1 Efficacy Assessments**

The efficacy of Proglucamune® on PQi and GQi status will be quantified as outlined in the PQD scoring system (Table 1 & Table 2) and the GQ scoring system (Table 3 & Table 4). Each subject's PQi and GQi status – as reflected in their PQD and GQD score – for each visit will be used to determine whether or not the subject's PQi or GQi status is improved by Proglucamune®. Treatment efficacy will also be evaluated by measuring and comparing salivary IgA levels at day 1 (Study Visit 1), day 42 (Study Visit 4) and day 84 (Study Visit 7).

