#### **9.4.2 Analysis of the Efficacy Endpoint(s)**

Trial outcome measures, if they are continuous, will be evaluated by skewness and kurtosis for normality and expressed as mean (95% CI) if both measures were within the range of (2, -2); otherwise they will be expressed as median (95% CI) with specification. Given the potential effect of treatment time on trial outcomes, we will analyze the effect of  $\beta$ -glucan with adjustment by treatment time. This will be conducted by linear mixed regression [16] or Aligned Rank Transformation ANOVA [17] if assumptions of the regression model were not satisfied. Categorical outcomes will be derived from conventional PQD diagnosis. The effect of  $\beta$ -glucan will be analyzed using generalized mixed linear model [18] for conventional PQD diagnosis.

For all statistical analyses, differences with a  $P < 0.05$  (two tailed) will be considered significant.

Other details analysis of the primary endpoints are described as follows:

- The PQi status of each participant at baseline and each follow-up visit will be measured by on-site investigators (licensed TCM practitioners) through a standardized quantitative assessment (Table 1 & Table 2). Each health condition relevant to PQD (i.e. cold frequency, symptoms, and signs) will be scored on a designed scale (ranging 1-10, with higher number indicating more severe deficiency) based on a set of standardized and specified criteria (Table 2). The sub-scores are then weighted (cold history 25%, symptoms 33.3%, signs: 41.7%) to arrive at a final PQD severity score. This score is on a 1-5 scale, with 5 being the most severe deficiency. The change of the score from baseline, indicating the treatment effect, will be calculated and analyzed by statistical means.
- PQi status of each participant at baseline and each follow-up visit will be measured by on site-investigators (licensed TCM practitioners) through non-standardized, qualitative traditional assessment. The status was characterized by non-PQD or PQD. The change of PQi status from baseline, indicating the treatment effect, will be calculated and analyzed by categorical statistic.

Other details analysis of the secondary endpoints are described as follows:

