**Table 2: Standardized criteria for PQi severity score assessment**

Candidate Parameter		Method of measurement and scores	
Cold Frequency	TCM Inquiry (Cold frequency)	No cold in the past 2 months	0
		Once in the past 2 months	1
		Twice in the past 2 months	2
		3 times or more in the past 2 months	3
Symptoms of PQD	TCM Inquiry (Spontaneous sweating)	No spontaneous sweating, sweat only with intense physical activities	0
		Sweat with routine physical activities	1
		Sweat heavily with routine physical activities	2
		Sweat with slight physical activities like walking	3
		Sweat spontaneously	4
	TCM Inquiry (Aversion to wind & cold)	No aversion to wind or cold	0
		Aversion to wind	1
		Aversion to cold, but relieved by adding light clothing	2
		Aversion to both cold (but relieved by light clothing) and wind, or susceptible to cold when exposed to wind or cold	3
		Aversion to cold (only relieved by thick clothing that covers whole body); or very easily catch a cold when exposed to wind or cold	4
Sign of PQD	TCM Auscultation (Low voice & apathy)	The participant's voice is loud & clear at a distance of 2m from the investigator	0
		The participant can be heard & understood at 2m from the investigator, but the voice is recognizably weak.	1
		The participant's voice is clearly low at 2m from the investigator & needs much attention to understand.	2
		The participant can be heard from 2m but need repeated clarification.	3
		The participant cannot be heard with a clear understanding at a distance of 2m.	4
	TCM Inspection (Tongue)	The tongue looks light red with thin white coating and is of proper size.	0
		The tongue looks pale in color with white coating; however, the tongue is of proper size & has no tooth mark on the sides.	1
		The tongue looks pale with white coating. This size is slightly larger than normal. Tooth-marks are visible but are limited to part(s) of the tip and sides of the tongue.	2
		The tongue looks pale with white coating. This size is significantly larger than normal. Tooth-marks are visible along the full length of the tip and sides of the tongue.	3
	TCM Palpation (Overall Pulse  )	Normal pulse	0
		Deficient Pulse is detectable but not apparent	1
		Apparent Deficient Pulse	2
	TCM Palpation (Cun Puls  )	Normal pulse	0
		The pulse shows characteristics of Floating or Deficient Pulse, but not both.	1
		Floating pulse is present, Deficient Pulse is detectable but not apparent.	2

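### LOCF is the only missing-data rule: it lets an earlier score stand in for week 12, dilutes a real effect, and biases the comparison in either direction if loss is unequal

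*Combined protocol and SAP*

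**What the plan says.** All references are to the combined protocol and SAP.

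- **Analysis set and missing data (9.3).** "The intention-to-treat analysis method will be followed for trial outcomes". For participants who withdraw or miss visits, "data from the previous visit will be used for the missing value (Last Observation Carried Forward, or LOCF"). This is the whole missing-data plan.
- **Endpoint (9.1).** The primary endpoint is "Change of Protective Qi after a total of 12 weeks follow-up".
- **Model (9.4.2).** The section expects treatment time to affect outcomes and adjusts for it: "This will be conducted by linear mixed regression [16] or Aligned Rank Transformation ANOVA [17] if assumptions of the regression model were not satisfied". A generalized mixed model is planned for the traditional PQD diagnosis.
- **Attrition (7.2.2, 7.2.2.2).** Planned at 20% overall, with no figure by arm.
- **Visits.** Every two weeks for 12 weeks (Appendix 1). Saliva IgA is measured only at "day 1 (Study Visit 1), day 42 (Study Visit 4) and day 84 (Study Visit 7") (8.1).
- **Score.** Cold history carries 25% of the PQD score (9.4.2, Table 1). Table 2 grades it over two months, the top grade being "3 times or more in the past 2 months".
- **Season (5.5).** "The enrollment will start in Dec. 2018 and concluded in March 2019".
- **Assessment on leaving.** Section 7.2.2 asks for the end-of-study evaluations at withdrawal where possible. Sections 7.1 and 7.2.2.2 list only safety laboratory tests, anthropometrics and vitals.

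**The concern.** LOCF is right on average only if a leaver's score would have stayed where it was. Several features of the plan point to a downward drift in both arms. Follow-up of a December-to-March cohort runs from about late February into June, and recent colds make up a quarter of the score. Section 4.2 acknowledges a placebo effect, and 9.4.2 allows for an effect of time. If scores do drift, a leaver is frozen at a higher (worse) point than week 12 would have shown.

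Three consequences follow:

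1. A real effect that builds over 12 weeks is diluted, even with equal loss.
2. Filled values enter the mixed model as if observed. They repeat earlier values exactly, so the within-person variance and the standard error come out too small.
3. If one arm loses more people, or loses them earlier, that arm looks worse at week 12 even when the product does nothing.

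For saliva IgA, a participant who leaves before day 42 without an exit sample has only the day-1 value to carry, and so counts as exactly zero change.

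**Working it through.** **Number of values affected.** Section 9.2 gives 49 per group (d = 0.8, alpha 0.01, power 0.9). A two-sided two-sample t-test gives 48.19, rounded up to 49, so the figure reproduces. Allowing for 20% loss, 49 / 0.80 = 61.25, rounded up to 62, which matches 4.1. At that loss about 0.20 × 62 = 12 participants per arm would have no week-12 score of their own.

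**Assumptions, since the documents give no figures.** 62 per arm, 7 visits, visit SD 0.5 points, between-visit correlation 0.6, both arms falling 0.5 points linearly, last attended visit spread evenly over Visits 1 to 6, and loss unrelated to outcome.

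**Share of the fall still to come at the last attended visit.** For Visits 1 to 6 the shares are 6/6, 5/6, 4/6, 3/6, 2/6 and 1/6. Their mean is u = 21/36 = 0.583.

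**Dilution with equal loss.** Effect under LOCF = true effect × (1 − loss × u) = 0.40 × (1 − 0.20 × 0.583) = 0.353. Simulation also gives 0.35.

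**False difference with no true effect** = (placebo loss − active loss) × common fall × u. The error rates are simulated, with a t-test on week-12 change and a nominal 5%.

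| Active / placebo loss | Common fall | Formula | False difference (points) | Error rate |
|---|---|---|---|---|
| 20% / 20% | 0.5 | 0 × 0.5 × 0.583 | 0 | about 5% |
| 15% / 25% | 0.5 | 0.10 × 0.5 × 0.583 | 0.03 | about 6% |
| 10% / 30% | 0.5 | 0.20 × 0.5 × 0.583 | 0.06 | 10–11% |
| 10% / 30% | 0.8 | 0.20 × 0.8 × 0.583 | 0.09 | about 18% |

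Swapping the arms reverses the sign: more placebo loss favours the product, and more active loss works against it.

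**Shape of the fall (10%/30%, 0.5 points).** If half the fall is complete by Visit 2 and half is linear, u = (1 + 0.417 + 0.333 + 0.25 + 0.167 + 0.083) / 6 = 0.375. The false difference is then 0.20 × 0.5 × 0.375 = 0.04 points, with about 8% error. If the whole fall is complete by Visit 2, u = 1/6, the difference is 0.017 points and the error rate is 5–6%.

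**Mixed model on LOCF-filled visits.** Section 9.4.2 does not state the random effects, so a random intercept is assumed. At 20%/20% loss and no effect, the model's standard error averages 0.0777 against an actual 0.0814, which is about 5% too small. Rejection is about 6%. At 15%/25% and 10%/30% loss it is about 8% and 13%, somewhat above the t-test figures.

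**Same data without filling.** A likelihood analysis of the observed visits only, with the covariance treated as known, gave bias of about 0 and rejection of 4.2–5.1%. It recovered the 0.40 effect as 0.40.

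**The case against.** The case for leaving the rule alone has force in several places.

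- **Carried scores are not largely pre-treatment.** A reader might infer that they are from the two-month look-back. With a 60-day window, the share of the cold item falling before the first tablet is (60 − 14)/60 = 77% at day 14, 53% at day 28, 30% at day 42, 7% at day 56 and nil from day 70. But that item is 25% of the score, so the first two figures become 19% and 13% of the total weight. The other items in Table 2 have no such look-back.
- **Most carried scores are not baseline scores.** A missed middle visit leaves week 12 untouched, a missed last visit carries week 10, and only someone lost before Visit 2 carries baseline.
- **Regression to the mean adds little.** Entry above 1.8 makes it likely, and 9.2 corrected the pilot for it. It should show mostly by the first visit after baseline, so it matters mainly for those lost before Visit 2.
- **Unequal loss is not predicted.** The placebo matches in appearance and taste (4.2), and risk is described as minimal (2.3.1).
- **The bias is modest beside the design effect.** With the assumed SD of 0.5, 0.03 to 0.06 points is 0.06 to 0.12 SD, against 0.8 SD in 9.2.
- **Exit assessments may be done.** If the 7.2.2 evaluations take place, an early leaver could have a saliva sample. The narrower lists in 7.1 and 7.2.2.2 leave this open.

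All of this limits the size of the problem and stands. None of it justifies the rule. Dilution and understated standard errors do not need unequal loss, an exit score still describes the exit date rather than week 12, and the planned models do not need complete data.

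**Conclusion.** The point holds as a weakness of method with a small to moderate effect. LOCF is the sole rule, the documents give reasons to expect drift in both arms, and the planned analysis can work without filling.

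With equal 20% loss, the cost is a diluted effect (0.40 to 0.35 points) and an error rate of about 6% in a random-intercept model. Unequal loss adds a false difference of about 0.03 points at 15%/25% and 0.06 points at 10%/30%, in either direction. These sizes depend on the assumed SD, correlation, linear fall and evenly spread loss, and they shrink if the fall comes early.

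A reader might go further and conclude that the trial will show a spurious benefit. The documents do not support that: they give no loss by arm, and the bias could equally run against the product. The zero-change point for saliva IgA holds only for leavers before day 42 with no exit sample.

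**What to change.** In 9.3, remove LOCF as the primary handling. State that the linear and generalized mixed models of 9.4.2 will be fitted to all observed visits of all randomised participants, with treatment-by-visit terms and the week-12 contrast as the primary comparison. Include values observed after stopping tablets, since 7.1 keeps such participants in the study. Say how the Aligned Rank Transformation fallback will treat incomplete data.

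Apply the same rule to the GQD score, saliva IgA and the questionnaires. Report withdrawal by arm, with timing and reason. Keep LOCF as a labelled sensitivity analysis for comparison with the pilot. Reconcile 7.2.2 with 7.1 and 7.2.2.2 on which efficacy measures are attempted at withdrawal.

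The analysis change is wording only and needs no new data. The document is dated February 2022 and enrolment was due to end in March 2019, so if unblinded results have already been seen, declare the change as later and show both analyses. The downsides are somewhat wider intervals, reliance on data being missing at random (the simulations above took loss as unrelated to outcome, so they do not test this), and less direct comparability with the pilot, which used LOCF.

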### 9.4 Statistical Analyses

#### 9.4.1 General Approach

Kolmogorov-Smirnov Test for Normality will be performed to check whether continuous baseline values are normal distribution. Continuous variables with normal distribution will be reported as mean and standard deviation (SD) and tested by t-test, otherwise will be reported as median and Interquartile range (IQR) and tested by Kruskal-Wallis rank sum test. Categorical variables will be presented as the participants' number and proportion (%) and tested by Chi-square or Fisher's exact test.

#### **9.4.2 Analysis of the Efficacy Endpoint(s)**

Trial outcome measures, if they are continuous, will be evaluated by skewness and kurtosis for normality and expressed as mean (95% CI) if both measures were within the range of (2, -2); otherwise they will be expressed as median (95% CI) with specification. Given the potential effect of treatment time on trial outcomes, we will analyze the effect of  $\beta$ -glucan with adjustment by treatment time. This will be conducted by linear mixed regression [16] or Aligned Rank Transformation ANOVA [17] if assumptions of the regression model were not satisfied. Categorical outcomes will be derived from conventional PQD diagnosis. The effect of  $\beta$ -glucan will be analyzed using generalized mixed linear model [18] for conventional PQD diagnosis.

For all statistical analyses, differences with a  $P < 0.05$  (two tailed) will be considered significant.

Other details analysis of the primary endpoints are described as follows:

- The PQi status of each participant at baseline and each follow-up visit will be measured by on-site investigators (licensed TCM practitioners) through a standardized quantitative assessment (Table 1 & Table 2). Each health condition relevant to PQD (i.e. cold frequency, symptoms, and signs) will be scored on a designed scale (ranging 1-10, with higher number indicating more severe deficiency) based on a set of standardized and specified criteria (Table 2). The sub-scores are then weighted (cold history 25%, symptoms 33.3%, signs: 41.7%) to arrive at a final PQD severity score. This score is on a 1-5 scale, with 5 being the most severe deficiency. The change of the score from baseline, indicating the treatment effect, will be calculated and analyzed by statistical means.
- PQi status of each participant at baseline and each follow-up visit will be measured by on site-investigators (licensed TCM practitioners) through non-standardized, qualitative traditional assessment. The status was characterized by non-PQD or PQD. The change of PQi status from baseline, indicating the treatment effect, will be calculated and analyzed by categorical statistic.

Other details analysis of the secondary endpoints are described as follows:

- The GQi status of participants at baseline and each follow-up visit will be assessed by on-site investigators (licensed TCM practitioners) through a standardize quantitative assessment (Table 3 & Table 4). Each health condition relevant to GQi Deficiency (GQD) (including symptoms, and signs) will be scored based

on a standardized criteria (Table 4), and then weighted to arrive at a final GQi severity score (Table 3). This score is on a 1-5 scale, with 5 being the most severe deficiency. The change of the score from baseline, indicating the treatment effect, will be calculated and analyzed by statistical means.

- The participants' Global Health will be assessed using the established PROMIS® Scale v1.2 (Please see the link <https://www.healthmeasures.net/explore-measurement-systems/promis> ). This questionnaire consists of 10 global-health related questions. The answer for nine of ten questions are graded on 1-5 scale (with 5 being the best), and one question is graded on 1 to 10 scale (with 10 being the worst grade). The sub-scores are used to obtain a final combined score of Global Physical Health or Global Mental Health using a T-score metric in which 50 is the mean of a relevant reference population and 10 is the standard deviation (SD) of that population. The change of the score from baseline, indicating the treatment effect, will be calculated and analyzed by statistical means.
- The effect of Proglucamune on the participants' immunity will be assessed by the change of saliva secretary IgA, which will be normalized by the secretion rate ( $\mu\text{g}/\text{min}$ ). The change of the score from baseline, indicating the treatment effect, will be calculated and analyzed by statistical means.
- Neuro-QoL (Quality of Life in Neurological Disorders) is a measurement system that evaluates and monitors the physical, mental, and social effects experienced by adults and children living with neurological conditions. Please see the link (<http://www.healthmeasures.net/explore-measurement-systems/neuro-qol>) for details. This questionnaire consists of 8 questions related to emotional and behavioral control. The answers for each of the questions are graded on five levels from best to worst. A combined score is generated using a T-score metric in which 50 is the mean of a relevant reference population and 10 is the standard deviation (SD) of that population.
- The participants' Emotional status will be assessed using the ASCO-Me® v2.0 Emotional Impact (Short Form). This questionnaire-based survey was established based on a Sickle-cell patient population (Please see the link <http://www.ascq-me.org/Science> or the citation below for detail). This questionnaire consists of 5 emotional-status related questions. The answer for each of the questions are graded on five levels from best to worst. A combined score is generated using a T-score metric in which 50 is the mean of a relevant reference population and 10 is the standard deviation (SD) of that population.

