## **5. Study Population**

### **5.1 Inclusion Criteria**

1. Male or females aged 18 to 65 years (inclusive) without regard to race or ethnic background
2. Provide a signed Informed Consent prior to entry in the study.

3. Willing to follow all study instructions and consume the assigned investigational product for 12 weeks.
4. Not currently taking a  $\beta$ -glucan containing supplement or any other supplement that might interfere with the study design.
5. Ability to swallow tablets and pills.
6. Exhibit a PQD severity score  $> 1.8$  (calculated by Table 1 & Table 2)

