## **6.3 Measures to Minimize Bias: Randomization and Blinding**

This study will be a randomized, triple-blind, placebo-controlled, parallel arm design. The participants will be recruited and randomized in a 1:1 ratio to either of two interventions: 1) Daily consumption of the control supplement (placebo), and 2) Daily consumption of the treatment ( $\beta$ -glucan). For randomization, these participants will be first stratified based upon: 1) ethnicity, 2) whether or not the subject has had an influenza vaccine (flu shot) since October 1, 2018, and 3) whether or not the subject currently exhibit a 'cold' as defined by TCM (hereafter referred to as cold\*). These factors will be deemed potential confounders of  $\beta$ -glucan effect. Throughout the trial, including the recruitment and the treatment, all participants and on-site investigators will be blinded to treatment.

Each participant has an emergency envelop, the information of this participant's allocation (treatment group or placebo group) will be include in, and PI will hold onto the envelops. If any participant needs to be unblinded, PI will open the corresponding envelop and notice the relevant physician.

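### The primary mixed model names only treatment time: baseline score and the three stratification factors are not covariates, and no contrast is tied to the 12-week change

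*Combined protocol and SAP*

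**What the plan says.** All references are to the combined protocol and SAP.

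- **Endpoint.** Section 9.1 declares the primary endpoint as "Change of Protective Qi after a total of 12 weeks follow-up".
- **Model.** Section 9.4.2 studies the effect of β-glucan "with adjustment by treatment time. This will be conducted by linear mixed regression [16", with an aligned-rank ANOVA as fallback. It lists no arm-by-visit term, no time-point contrast, no baseline covariate and no within-subject covariance.
- **Role of baseline.** The primary-endpoint bullet in section 9.4.2 says: "The change of the score from baseline, indicating the treatment effect, will be calculated and analyzed by statistical means". The score is taken at baseline and at every follow-up visit. The text does not say whether the baseline value is also a response in the model.
- **Traditional diagnosis.** This binary outcome "will be analyzed using generalized mixed linear model [18] for conventional PQD diagnosis". No covariates are listed.
- **Stratification.** Section 6.3 states: "For randomization, these participants will be first stratified based upon: 1) ethnicity". It then adds influenza vaccination and a current cold as TCM defines it, and says of all three: "These factors will be deemed potential confounders of" the β-glucan effect. Sections 9.3 and 9.4 do not mention them again.
- **Sample size.** Section 9.2 "obtained a minimal sample size of 49 for each group". Section 4.1 plans 62 per group.

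**The concern.** Two questions arise: which quantity is the primary result, and how precisely it is estimated.

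First, if time enters only as an adjusting main effect, the arm coefficient is a difference averaged over all visits. Section 9.1 asks for the change at 12 weeks. The two agree only if the effect is constant across visits. An analyst could report either and stay within section 9.4.2.

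Second, the plan collects variables that usually sharpen the comparison and does not use them as covariates. Subtracting baseline is less efficient than adjusting for it. When randomisation is stratified on factors that predict the outcome, an analysis that ignores them gives standard errors that are too large. In the mixed logistic model for the traditional diagnosis, omitted prognostic factors can also pull the conditional odds ratio toward 1.

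**Working it through.** **Inputs from the documents.** 49 per group at alpha 0.01, power 0.9, effect 0.8 (section 9.2); 62 per group (section 4.1); 20% attrition (section 7.2.2); two-tailed 0.05 (section 9.4.2); visits every 2 weeks to week 12, so six after baseline (Appendix 1); enrolment only above a score of 1.8 (section 5.1, "Exhibit a PQD severity score"). The documents give no pre-post correlation, no strata effect, no share of scores cut by the entry rule and no time course. Those are assumptions below.

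**1. The plan's own figure.** A two-sided two-sample t-test with d = 0.8, alpha 0.01 and power 0.9 needs 48.19, so 49 per group. It reproduces. 49/0.8 = 61.25, rounded up to 62. This is a single two-group comparison and does not show which model term was meant.

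**2. Change score versus baseline covariate at week 12.** Let r be the correlation before selection and Vx the share of baseline variance left after the entry cut (normal scores). Variance ratio = 1 + Vx(1−r)/(1+r).

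| Share cut (assumed) | Vx | r = 0.3 | r = 0.5 | r = 0.7 |
|---|---|---|---|---|
| 10% | 0.712 | 1.38 | 1.24 | 1.13 |
| 50% | 0.363 | 1.20 | 1.12 | 1.06 |

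The plain change score therefore has 6% to 38% more variance. Most of that goes if baseline is a response row with a common mean in both arms.

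**3. What this does to power at 62 per group, two-sided 0.05.**
- If 0.8 is in change-score SDs, the plain change score has power 0.99.
- If 0.8 is in score SDs and r = 0.3, d = 0.8/√(2(1−0.3)) = 0.676 and power is 0.96.
- With the baseline covariate in that second case, d = 0.8/√(1−0.3²) = 0.839 and power is 0.996. This ignores the entry cut, which favours the covariate.

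**4. Strata ignored after balanced stratified randomisation.** If the strata explain a share R² of the change score, estimated/true variance = 1/(1−R²) and type I error = 2[1−Φ(1.96/√(1−R²))].

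| R² (assumed) | Variance overstated by | Type I error |
|---|---|---|
| 0% | 0% | 0.050 |
| 5% | 5% | 0.044 |
| 10% | 11% | 0.039 |
| 20% | 25% | 0.028 |

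The true variance of the estimate is hardly affected; the test is conservative.

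**5. Visit average versus week 12, days 14 to 84.**
- Linear build-up: (1+2+3+4+5+6)/(6×6) = 0.58 of the week-12 effect.
- Plateau by day 28: (0.5+5)/6 = 0.92.
- Immediate and constant: 1.00.

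At 62 per group, with d = 0.8 at week 12 and equal correlation between visits (normal approximation), the week-12 contrast has power 0.994. Under linear build-up the visit average has power 0.925 at correlation 0.5 and 0.851 at 0.7. If the effect is immediate, the visit average has power of at least 0.999.

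**6. Is an immediate effect on the score plausible?** Cold frequency carries 25% of the score (Table 1) and is counted over the past 2 months (Table 2). With a 60-day window, the share of the window on treatment at days 14 to 84 is 0.23, 0.47, 0.70, 0.93, 1 and 1, averaging 0.72. For this component some delay is built in, even if colds fell at once.

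**The case against.** - **Baseline is not ignored.** A reader might infer that it is left out of the analysis. The documents do not support that: it is subtracted, and it may also be a response row, since the score is analysed at baseline and follow-up. What is missing is its use as a covariate. This objection stands.
- **An arm-by-visit term is not excluded.** Adjusting for time is compatible with an interaction, so it would be too strong to say that the model cannot estimate the 12-week change. The defect is that no contrast is named.
- **Stratified randomisation already deals with the factors by design.** For bias this is right. A reader might take the label of potential confounders to mean that the unadjusted comparison is confounded, but randomisation rules that out. It does not make the standard error correct if the strata predict change.
- **The strata may explain nothing.** A factor that shifts the score equally at all visits cancels in a change score, hence the 0% row. A current cold may not cancel: it would presumably count in the 2-month window at baseline and, once over, leave it before day 84. The size is unknown.
- **The cost is small.** At 62 per group and the planned effect this holds. The case for the covariates is that they cost almost nothing.

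**Conclusion.** The point holds as an incomplete specification with a modest loss of efficiency. The unnamed contrast weighs most: two analyses that both fit section 9.4.2 can target quantities that differ by anything from nothing (immediate effect) to 42% of the week-12 effect (linear build-up). The missing covariates cost 6% to 38% in variance at week 12 and make the test conservative to the extent that the strata predict change. All these figures rest on the assumptions stated above.

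Two stronger inferences fail. The omissions do not bias the continuous randomised comparison or inflate its type I error. They also do not leave the trial underpowered for the planned effect at week 12, where power is 0.96 or more in the cases worked.

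For the mixed logistic model only the direction, toward an odds ratio of 1, can be stated. The plan gives neither its random-effect structure nor the strength of the factors, so no figure is offered.

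**What to change.** In section 9.4.2, model the post-baseline PQD scores on arm by visit, baseline score by visit and the three stratification factors (sparse ethnicity levels pooled), with a stated within-subject covariance. Name the arm difference at day 84 as the primary contrast, to match section 9.1, and the visit average as secondary. Add the strata to the mixed logistic model where it converges.

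**Cost.** The variables are already collected, so this is SAP wording and code. It uses a few degrees of freedom, and some strata may be sparse.

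**Timing.** Section 5.5 ends enrolment in March 2019. From 31 March, 84 days run to 23 June 2019, about 32 months before version 4.0 (18 February 2022). The documents do not say when data were unblinded. If that came before version 4.0, label the adjusted model as a sensitivity or post hoc analysis.

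The last-observation-carried-forward rule in section 9.3 is a separate matter and should be handled as its own point.
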